10. STUDY ASSESSMENTS AND PROCEDURES

EFFICACY ASSESSMENTS

The main drug efficacy measure for this study is neurodegeneration (secondary objective). We will derive annual brain atrophy rates by comparing volumetric MRI (vMRI) values for the hippocampal, cortical, and global thickness. All 105 study participants will undergo vMRI at Baseline (Week 0) and after 6 months, 12 months, and 18 months.

To demonstrate clinical utility, it is necessary to show that a possible treatment for AD can slow down or reverse cognitive decline. Thus, our tertiary objective (and secondary efficacy endpoint) will assess cognition in all study subjects. For this, we will employ the recently created, high-sensitivity

Alzheimer’s Disease Composite Score (ADCOMS), which is recommended for mild AD in clinical trials of 12 months’ duration or longer⁴¹. Briefly, ADCOMS consists of 4 Alzheimer’s Disease Assessment Scale-cognitive subscale items (ADAS-Cog13), 2 Mini-Mental State Examination items (MMSE), and all 6 Clinical Dementia Rating-Sum of Boxes items (CDR-SOB)⁴¹. ADCOMS will be administered at specified time points throughout the study (refer to study table 1). Furthermore, to assess conversion to AD or reversion to normality, we will repeat the cognitive measurements at 18 months (Week 78). This time was selected because the calculated mean time for conversion from aMCI to AD in the literature ranges from 12-20 months¹⁶. Thus, measuring cognitive performance 18 months after the start of the trial should provide us with a good assessment of whether Sisonimod is effective at slowing down cognitive decline. A positive effect of Sisonimod on cognitive outcome measures would translate into increased ADCOMS scores at the end of dosing vs. Baseline and/or a slower decline than in placebo-treated subjects at month 18.

Additional objectives (exploratory efficacy endpoints) are (i) an additional assessment of cognitive performance via the ADCS-ADL test administered every 6 months; and (ii) the measurement of biomarkers in the CSF, blood, and saliva, to explore the possibility of using biofluid markers as proxy of drug efficacy. For example, since Sisonimod is an immunomodulator that prevents the egression of T lymphocytes from peripheral lymphoid organs, we should observe a decrease in circulating T lymphocytes and inflammatory markers in the blood samples we collect during the entire course of this clinical trial.

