All procedures are carried out by trained medical staff and scientists used to conduct clinical trials at the study site. Labs (CBC with differential and CMP) analyses are performed by a contracted medical laboratory, therefore follow GCP standards.

+ Neurodegeneration Measures

- Volumetric MRI

MR imaging will be conducted on a 3T MRI scanner located in Phoenix, AZ. Sequences will include a high resolution 3D T1-weighted magnetization prepared rapid acquisition gradient echo (MPRAGE), a T2-weighted image, a 3D FLAIR image, and a high-resolution T1 image of the hippocampus. Each individual scan will be less than 7 minutes in length and will match protocols developed by the Alzheimer’s disease neuroimaging initiative (ADNI). Other imaging may include advanced diffusion and perfusion . Each of these scans will be less than 10 minutes in duration, and the overall scan time will be less than 1 hour.

40 min sequence (estimated 38 min 26 s)

Sequence	Approx. run time in minutes
T1-weighted MPRAGE	6:11
T2-weighted image	6:42
T2-weighted FLAIR	6:10
High Res Hippo	5:36
Diffusion MRI	8:05
Perfusion MRI	5:32

+ Cognitive Measures

- Alzheimer’s Disease Assessment Scale - Cognitive

Alzheimer’s Disease Assessment Scale - Cognitive (ADAS-cog)³⁶ is a psychometric instrument that evaluates memory, attention, reasoning, language, orientation, and praxis. A higher score indicates more impairment; the range is 0 to 89. We will use the ADAS-cog13 as it is the currently accepted scale used by clinicians to detect changes in mildly demented subjects.

- Clinical Dementia Rating-Sum of Boxes

The Clinical Dementia Rating - Sum of Boxes (CDR-SOB) test³⁴ is a commonly used instrument in MCI studies. The CDR-SOB describes five degrees of impairment in performance on each of 6 categories of cognitive functioning including memory, orientation, judgment and problem solving, community affairs, home and hobbies, and personal care. The ratings of degree of impairment obtained on each of the 6 categories of function are synthesized into one global rating of dementia (ranging from 0 to 3), with more refined measure of change available by use of the Sum of Boxes. The CDR-rater will be a trained clinician. Ideally the same CDR rater will be used throughout the course of the trial when possible.

- Mini Mental State Examination

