The Mini Mental State Examination (MMSE) is a screening instrument frequently used in Alzheimer's disease drug studies.¹¹ It evaluates orientation, memory, attention, concentration, naming, repetition, comprehension, and the ability to create a sentence and copy two intersecting pentagons. Scores range from 0 to 30, with 30 being the score assigned to cognitively normal individuals. The range for mild AD is 21-26.

- Alzheimer's Disease Cooperative Study - Activities of Daily Living

In the Alzheimer's Disease Cooperative Study - Activities of Daily Living (ADCS-ADL) test, study partners are queried via a structured interview format as to whether subjects attempted each item in the inventory during the preceding four weeks, as well as their level of performance¹⁴. This will provide a reliable estimate of daily functioning. ADCS-ADL is not part of the ADCOMS computation. It will be administered every 6 months, as done routinely for our clinical trials.

- ADCOMS

The AD Composite Score (ADCOMS) consists of 4 ADAS-Cog items, 2 MMSE items, and all 6 CDR-SOB items [PMID: 27010616]. The ADCOMS was derived with the intention of using it as a primary outcome measure for registration trials of disease-modifying treatments in persons with predementia and early AD-related dementia. The ADCOMS has demonstrated improved sensitivity over each individual scale comprised in the composite and requires smaller sample sizes to detect longitudinal cognitive changes. Retrospective analyses have shown that ADCOMS is superior to other measures in detecting and measuring early cognitive decline and disease progression among patients with early stages of AD, i.e. mild cognitive impairment and mild AD [PMID: 35099758]. Thus, the ADCOMS appears as the most promising cognitive composite score for the present study.

+ Biomarkers

- Exploratory Blood Biomarkers

Because CSF collection is not possible at each site visit, we explore the possibility of using blood inflammatory markers as surrogate markers of Sisonimod efficacy. For this, we will collect whole blood (cubital vein); maximum 45 mL in tubes containing ethylenediaminetetraacetic acid (EDTA). After differential centrifugations, we will measure plasma C-reactive protein, TNF- α , IL-1 β , IL-6, IL-8, and IL-10 by multiplex ELISA (Meso Scale Discovery 54 Plex for human inflammatory markers).

+ Exploratory Saliva Biomarkers (Optional Sub-Study)

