12. STATISTICAL CONSIDERATIONS

STATISTICAL HYPOTHESES

- Primary and Exploratory Efficacy Endpoint(s):

The null hypothesis for the primary efficacy endpoint is that biomarker measures (primary endpoint: vMRI; tertiary and exploratory endpoints: CSF biomarkers, blood inflammatory markers, saliva amyloid beta levels) will be the same in Siponimod- vs. placebo-treated study subjects after 12 months (end of dosing).

The alternative hypothesis is that Siponimod will improve biomarker measures at the same time point.

- Secondary Efficacy Endpoint(s):

The null hypothesis for the secondary efficacy endpoint is that cognitive measures (ADCOMS) will be the same in Siponimod - vs. placebo-treated study subjects after 12 (end of dosing) and 18 months (6 months follow up).

The alternative hypothesis is that Siponimod will improve cognitive measures at the same time points.

SAMPLE SIZE DETERMINATION

Mild AD subjects will receive an escalating dose of Siponimod up to 1 mg/day (N=70) or placebo (N=35) for 12 months (Table 2). We conducted a power analysis for sample size determination using the reported data from brain volume changes in SPMS subjects treated for at least 12 months with Siponimod or placebo²⁵. We wished to fit a repeated measures ANOVA model with two treatment levels in drug vs. placebo, and 4-time measures to receiving the drug (i.e. vMRI at baseline, 6, 12, and 18 months). We defined $Y_{ij} = \mu + \alpha_i + \tau_j + (\alpha\tau)_{ij} + \varepsilon_{ijk}$, where Y_{ijk} denotes the measure on brain atrophy, α_i denotes the treatment effect $i = 1, 2$; τ_j denotes the time effect at time $j=1, 2, 3, 4$; $k = 1, n$; $(\alpha\tau)_{ij}$ is the interaction between time and treatment; and ε_{ijk} is the error term²¹. We study the effect of the drug on brain atrophy. The between-subject factor in our model is treatment, with two levels (study drug and placebo), and we allocate each treatment in the ratio 2:1. The within-subject factor is time, with four levels (0, 6, 12, and 18 months). The number of patients needed is determined to achieve a power of 0.90 at significance level $\alpha = 0.05$ for the test of the interaction between time and treatment, where the contrast over time contains all pairwise comparisons. We also intend to generate a plot of power versus sample size that covers the power range of 0.05 to 0.90.

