Statistical analysis of the biomarkers and clinical assessments will be carried out by our biostatistician. Comparisons will assess the change from baseline for the following markers assessed at the frequency indicated in the schedule of visits Table 1):

- vMRI, which is used to estimate the annual rate of brain atrophy.

ANALYSIS OF THE SECONDARY ENDPOINT(S)

Statistical analysis of the biomarkers and clinical assessments will be carried out by our biostatistician. Comparisons will assess the change from baseline for the following markers assessed at the frequency indicated in the schedule of visits Table 1):

- Alzheimer's Disease Assessment Scale - Cognitive (ADAS-Cog13);
- Clinical Dementia Rating-Sum of Boxes (CDR-SOB);
- Mini Mental State Examination (MMSE);
- ADCOMS, which is calculated using components of the three cognitive tests indicated above.

SAFETY ANALYSES

- Concomitant Medications

Concomitant medications will be coded by the World Health Organization (WHO) Drug Dictionary and tabulated by the treatment group.

- Adverse Events

The incidence of all treatment-emergent AEs (TEAEs) and treatment-related AEs will be tabulated by treatment received. These AEs will be classified by system organ class and preferred term using the Medical Dictionary for Regulatory Activities (MedDRA). For incidence reporting, if a subject reported more than one AE that was coded to the same system organ class or preferred term, the subject will be counted only once for that specific system organ class or preferred term. A TEAE is defined as an event that first occurs or worsens in intensity after the administration of study drug. Events recorded between the time the informed consent is signed and the first study drug administration will be listed.

An overview of AEs, which includes subject incidence of TEAEs, treatment-related AEs, SAEs, deaths, and AEs leading to discontinuation, will be presented. For AEs presented by severity, the worst severity during the study will be presented for each subject.

The subject incidence of TEAEs and treatment-related AEs will be summarized by system organ class and preferred term.

- Serious Adverse Events

All SAEs will be listed and summarized in a similar manner to AEs.

- Clinical Laboratory Results

Clinical laboratory values will be measured by a central laboratory.

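### The protocol describes a rise in ADCOMS as benefit, against its own component scales, and plans to assess conversion to AD in patients who must already have AD dementia

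*Protocol*

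**What the plan says.** **Direction of ADCOMS.** Section 10, Efficacy Assessments, says that a positive effect of the drug on cognition "would translate into increased ADCOMS scores at the end of dosing vs. Baseline and/or a slower decline than in placebo-treated subjects" at month 18. Under Cognitive Measures the same section says that ADCOMS "consists of 4 ADAS-Cog items, 2 MMSE items, and all 6 CDR-SOB items". It describes the three source scales as follows:

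- ADAS-Cog: "A higher score indicates more impairment; the range is 0 to 89".
- CDR-SOB: "The CDR-SOB describes five degrees of impairment in performance on each of 6 categories of cognitive functioning". The boxes are called "The ratings of degree of impairment obtained on each of the 6 categories of function" and feed a global dementia rating from 0 to 3.
- MMSE: 0 to 30, "with 30 being the score assigned to cognitively normal individuals".

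Section 12, Analysis of the Secondary Endpoint(s), adds only "ADCOMS, which is calculated using components of the three cognitive tests indicated above". The hypothesis in section 12 compares ADCOMS on siponimod with that in "placebo-treated study subjects after 12 (end of dosing) and 18 months (6 months follow up"). Its alternative is that the drug improves cognition, with no sign given.

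**Conversion.** Section 10 says that cognition is repeated at Week 78 to assess conversion to AD or a return to normal. It chooses that time because published mean times from aMCI to AD are 12 to 20 months. Section 12, General Approach, plans an average conversion rate and a time-to-event analysis in the two groups. Inclusion criterion 3 in the synopsis requires a diagnosis of mild Alzheimer's dementia. Section 12, Sample Size Determination, explains why mild AD was preferred to MCI.

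**The concern.** The section 10 sentence is the only place in the protocol that attaches a sign to ADCOMS, and that sign disagrees with the scales from which the score is built. Its end-of-dosing limb is also a comparison with baseline, joined to the placebo comparison by and/or, so it can be read as sufficient alone. A treated arm that progressed in the usual way would then fit the description of a positive effect. Section 6 treats a change in the course of cognitive decline as the only clinical validation of improvement and includes ADCOMS for that purpose, so its direction should be beyond doubt before unblinding.

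The conversion text raises a separate problem: an event that every enrolled subject has already had cannot be assessed during follow-up. A rate or a time-to-event analysis built on it would have nobody at risk.

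**Working it through.** The protocol states no figure for this point. The check is an item count, a property of the test statistic, and a comparison of dates and populations.

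**1. Item count** (section 10, Cognitive Measures)

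| Source | Items | Higher score means | Basis in the protocol |
|---|---|---|---|
| ADAS-Cog | 4 | more impairment | stated |
| CDR-SOB | 6 | more impairment | follows from the description |
| MMSE | 2 | better cognition | 30 is normal |

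Total: 4 + 6 + 2 = 12. Higher is worse: 4 + 6 = 10, and 10/12 = 83%. Higher is better: 2/12 = 17%. This counts items and says nothing about weights, which the protocol does not give.

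**2. What would have to be reversed.** The components run in opposite directions, so any coherent composite must reverse one set. If a higher ADCOMS is worse, 2 of 12 items are reversed. If a higher ADCOMS is better, 10 of 12 are. The protocol states neither. The section 10 sentence needs the second.

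**3. Effect on the planned comparison.** Let Y be the ADCOMS change and t = (mean on drug − mean on placebo) / SE. Replacing Y by −Y changes the sign of the numerator and leaves SE as it was, so t becomes −t. |t| and the two-sided p-value are unchanged. The direction decides only how the result is read.

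**4. Effect on the baseline limb.** If a higher score is worse, progression gives a change from baseline above 0, which section 10 describes as a positive effect.

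**5. Subjects at risk of conversion to AD.** Planned enrolment is 105, all with AD dementia under inclusion criterion 3. At risk: 105 − 105 = 0. The footnote to the eligibility criteria allows individual waivers, so this holds by definition of the population and not necessarily for every subject.

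**6. Timing of month 18.** Day 546 − Day 364 = 182 days = 26 weeks, and Week 78 − Week 52 = 26 weeks. Sections 5 and 8 already set a 6-month washout after 12 months of dosing. The visit needs no support from aMCI conversion times.

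**The case against.** The strongest reply is that the inversion is inferred. The protocol gives no ADCOMS weights, sign or algorithm; scoring detail is commonly left to the SAP or the cited source, and an item count is not a weight. This stands. A reader might infer that the protocol proves the score is inverted, or that the test will be run in the wrong direction. The text supports neither: it shows a conflict with the component descriptions and no stated reversal.

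Second, the sentence is an expectation and governs no test. The hypothesis in section 12 is between arms. This also stands, as does the point that change from baseline is a legitimate measure: section 4 and the secondary-endpoint analysis both use it. The limb that compares with placebo is sound if decline means clinical decline. A reader might also infer that a paired within-arm test of ADCOMS is planned, but the paired tests in General Approach are specified for biomarkers. Section 12 does, in Populations for Analyses, use that word for cognitive performance, so the point is not wholly clear, but no within-arm ADCOMS test is specified.

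Third, General Approach does not name AD as its conversion event, and defining an event is ordinary SAP content. This stands in part. It would go too far to say that the time-to-event analysis must be deleted, since it could be given a possible event. But the protocol names no conversion other than to AD, and an SAP cannot make that event possible in this population. Nor does eligibility rule out a return to normal cognition; that part of the section 10 sentence is not challenged.

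**Conclusion.** The point holds as two wording errors that should be corrected. The stated direction of ADCOMS benefit conflicts with scales that supply 10 of its 12 items, and conversion to AD has nobody at risk, waivers aside. The first conclusion rests on the protocol's scale descriptions and on the absence of any stated reversal; the second rests on inclusion criterion 3. Confidence is moderate, because the scoring algorithm is not shown.

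The consequence is limited to how the tertiary objective (the secondary efficacy endpoint) is interpreted. It would be wrong to infer that the trial's inference is damaged: the safety objective, the vMRI analysis, power and sample size are untouched, and month 18 remains a justified visit.

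**What to change.** - **Section 10, Efficacy Assessments, direction.** State the direction of ADCOMS according to the scoring algorithm that will be used. Define benefit as less clinical worsening, or improvement, relative to placebo at months 12 and 18, which matches the section 12 hypothesis and is correct whichever way the score runs. Change from baseline may stay as the measure, but a within-arm increase should not be described as benefit.
- **Section 10, conversion.** Delete the conversion-to-AD purpose and the aMCI rationale. Justify month 18 as the end of the 6-month washout.
- **Section 12, General Approach.** Tie the conversion rate and time-to-event analysis to an event that can occur in mild AD dementia and uses data already collected, with its definition in the SAP, or drop it.

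The cost is wording in two sections. No visit, test or data collection changes, because the ADCOMS components are already collected at baseline and Weeks 24, 40, 52 and 78. The change should be made before unblinding, since correcting the direction of benefit once results are known would look post hoc.

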1. PROTOCOL SUMMARY

SYNOPSIS

Title:	SIPO1-AD: A Phase II Clinical Trial for the Assessment of Safety, Tolerability, and Efficacy of Siponimod in Patients with Mild Alzheimer's Disease
Study Description:	
Alzheimer's disease (AD) is a neurodegenerative disorder with several complex neuropathologies suspected to develop sequentially but that overlap over time as symptoms progress to dementia. Thus, to be effective, future intervention strategies will likely require combination therapies or pleiotropic agents to tackle several AD molecular pathogenic pathways simultaneously. For more than a decade, our group has been exploring the repurposing of immunomodulators for AD. Recent discussions with collaborators who specialize in multiple sclerosis suggest that sphingosine-1-phosphate receptor (S1PR) modulators are strong candidates for repurposing in AD. Indeed, S1PR modulators are blood brain barrier (BBB) penetrant and display pleiotropic actions, including immunomodulation and neuroprotective properties. S1P is a versatile endogenous molecule that regulates several signaling pathways by binding to five G-protein-coupled receptors, which are expressed in high levels in cardiac, vascular, immune, and brain cells. This widespread localization of S1PR was the historical basis for Novartis Pharmaceuticals, Inc, to develop oral formulations of S1PR modulators for multiple sclerosis (MS), which proved successful and resulted in two marketed oral compounds (i.e., fingolimod and Siponimod).
 
In the present project, we intend to collaborate with Novartis to use the most recently FDA-approved S1PR modulator, Siponimod. Based on MS and animal experimentation literature, we hypothesize that Siponimod could alter the rate of neurodegeneration as measured by lowering the rate of brain atrophy in mild AD dementia subjects. In this Phase II, proof-of-concept, translational clinical study, mild AD dementia subjects will be randomized 2:1 and will receive gradual titration regimen of Siponimod starting at 0.25mg/day and increasing up to final dosage of 1 mg/day (N=70) or placebo (N=35) for 12 months. This will be followed by a 6-month washout period. Siponimod has demonstrated positive immunomodulatory and neuroprotective actions in MS patients, and because its toxicity profile is favorable for use in older individuals, Siponimod has a strong potential to alter markers of mild AD dementia pathology and disease trajectory.

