- Blood biomarkers
- Dispense study drug and drug diary
- Drug accountability
- Adverse event assessment

Visit 13 at Day 364 End of Study Drug Treatment (\pm 7 days)

The following tests and procedures will be completed in clinic:

- Concomitant medication reconciliation
- Drug accountability and drug diary
- Coagulation panel labs (PT, PTT, INR) to be completed pre-optional lumbar puncture (LP).
- Labs (CBC w/ diff, CMP, TSH)
- EKG
- Vital signs including weight
- Neuro and physical exam
- Blood biomarkers
- OCT Eye Exam
- Volumetric MRI (+4 weeks)
- Cognitive Assessments (MMSE, ADAS-Cog13, CDR-SOB, ADCS-ADL)
- Drug accountability and collect drug diary
- Adverse event assessment

The following are to be completed if participants opted into one, or both, of the optional studies:

- *Lumbar puncture (to measure CSF biomarkers) followed by phone check in 24hrs post-lumbar puncture*
- *Saliva collection*

Visit 14 at Day 392 (\pm 7 days)

The following tests and procedures will be completed in clinic:

- Concomitant medication reconciliation
- Labs (CBC w/ diff, CMP, TSH)
- EKG
- Vital signs including weight
- Neuro and physical exam
- Blood biomarkers
- Adverse event assessment

The following are to be completed if participants opted for the Saliva sub-study:

- *Saliva collection*

End of Study at Day 546 (\pm 7 days)

The following tests and procedures will be completed in clinic:

- Concomitant medication reconciliation
- Labs (CBC w/ diff, CMP, TSH)
- EKG
- Vital signs including weight
- Neuro and physical exam
- Volumetric MRI (\pm 4 weeks, patients can come before or after visit for end of study)
- OCT Eye exam
- Blood biomarkers
- Cognitive assessments (MMSE, ADAS-Cog 13, CDR-SOB, ADCS-ADL)
- Adverse event assessment

The following are to be completed if participants opted Saliva sub-study:

- *Saliva collection*

Unscheduled Visits

Unscheduled visits will be at the investigator's discretion. All unscheduled visits will include the following tests and procedures:

- EKG
- Vital Signs and Weight
- Neurological and Physical Exam
- Labs (CBC with differential, CMP, TSH)
- Blood Biomarkers
- Medication reconciliation
- Adverse Event Assessment
- OCT Eye exam (in the case of blurred vision or other ocular issues)

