4. OBJECTIVES AND ENDPOINTS

OBJECTIVES	ENDPOINTS
PRIMARY	
The primary objective of the study is to assess the safety and tolerability of Siponimod in mild AD dementia subjects.	Safety will be assessed at each study visit through completion of comprehensive tests and procedures aimed at monitoring for potential adverse events (AEs). Study staff will also gather direct reports from subjects regarding any adverse events.
SECONDARY	
The secondary objective of the study is to assess the effects of Siponimod on AD-associated neurodegeneration by deriving annual brain atrophy rates from volumetric MRI (vMRI).	Siponimod was observed to slow rates of brain atrophy in both RRMS and SPMS patients. Thus, the aim is to assess the medical benefits of the drug in mild AD dementia subjects by assessing whether brain atrophy slows with Siponimod treatment. Subjects will undergo volumetric MRI (vMRI) measurements of the hippocampus, cortical thickness, and global thickness as indicators of neurodegeneration.
TERTIARY	
The tertiary objective of study is to assess the effects of Siponimod on cognition following administration of study drug vs. placebo.	Cognition will be assessed by comparing the changes in two assessments: ADCS-ADL and ADCOMS from baseline to various visit timepoints, including Week 78 (End of Study).
EXPLORATORY	
Exploratory objectives will include:	
i) measurements of markers found in the CSF fluid that are known to be associated with mild AD dementia and inflammation before and after treatment	i) CSF biomarkers that will be assessed include amyloid beta 40 & 42, Tau, and Phospho-Tau.
ii) assessment of blood inflammatory markers before and after treatment	ii) Blood inflammatory markers include CRP, TNF- α , IL-1 β , IL-6, IL-8, and IL-10 (54-plex measured on the Meso Scale Discovery [MSD] ELISA platform). Plus, we will count the number of white blood cells (B and T lymphocytes, macrophages, etc) in the blood to estimate the impact of Siponimod on peripheral markers of the immune system.
iii) to assess levels of A β found in saliva samples collected before and after treatment with Siponimod vs. placebo	iii) Saliva markers that will be assessed are A β 40 and A β 2. Saliva A β levels is a recent biomarker that has been identified to study AD. Thus, we propose to explore the effects of Siponimod on A β 40 and A β 2 throughout the course of the study.

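### The protocol's description of a positive cognitive effect leaves out the placebo comparison at end of dosing and so contradicts its own ADCOMS hypothesis

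*Protocol*

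**What the plan says.** Protocol section 10, Efficacy Assessments, explains how ADCOMS will be read. A positive effect is expected to appear as "increased ADCOMS scores at the end of dosing vs. Baseline and/or a slower decline than in placebo-treated subjects at month 18". The sentence has two parts, joined so that either may count:

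- **End of dosing:** ADCOMS against the subjects' own baseline. No placebo comparator is named.
- **Month 18:** decline against placebo.

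Section 12, Statistical Hypotheses, says something else. Its null for the secondary efficacy endpoint is no ADCOMS difference between siponimod and "placebo-treated study subjects after 12 (end of dosing) and 18 months (6 months follow up" visit). The alternative keeps both times: "The alternative hypothesis is that Siponimod will improve cognitive measures at the same time points". Section 4 gives the tertiary objective as the "effects of Siponimod on cognition following administration of study drug vs. placebo".

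The timing comes from section 1.1: "Visit 13 at Day 364 End of Study Drug Treatment" and "End of Study at Day 546". The synopsis says of the 12 months of dosing, "This will be followed by a 6-month washout period".

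**The concern.** The protocol gives two accounts of what would show a cognitive benefit. Section 12 uses a randomised comparison on drug (Month 12) and another off drug (Month 18). Section 10 keeps only the off-drug one and replaces the on-drug one with a before-and-after comparison in the treated arm.

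That comparison can mislead in two ways, depending on the course of the disease:

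- If subjects decline, as section 2.1 expects, a drug that slows decline still leaves them worse than at baseline. The own-baseline part cannot recognise this, although the same paragraph of section 10 counts slowing as clinical utility.
- If both arms improve, for example through practice or placebo response, the own-baseline part attributes the gain to the drug.

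Cognition is a tertiary objective, but section 10 also calls it the secondary efficacy endpoint, and section 6 treats a change in cognitive decline as the only clinical validation of improvement. How a benefit is recognised therefore matters to how the trial will be read.

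**Working it through.** **1. Time off drug.** Dosing ends at Day 364 (Week 52) and the last cognitive assessment is at Day 546 (Week 78). (546 − 364)/7 = 26.0 weeks, and 78 − 52 = 26. This agrees with the protocol's 6-month washout.

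**2. The passages side by side.**

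| Place | Month 12 (end of dosing) | Month 18 |
|---|---|---|
| Section 10, Efficacy Assessments | own baseline | placebo |
| Section 12, Statistical Hypotheses | placebo | placebo |
| Section 4, tertiary objective | placebo | placebo |

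(Section 4 covers several visits up to Week 78 and names no single time.)

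**3. Does the analysis text settle it?** Section 12, Analysis of the Secondary Endpoint(s), says that comparisons will assess change from baseline and names no comparator. The General Approach plans paired tests of biomarkers before and after dosing, and Populations for Analyses puts cognitive performance under biomarkers. A within-arm reading is therefore not ruled out.

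**4. Error when either part counts, no shift from baseline.** Assumption: each part is tested at two-sided 5%, so a false favourable result has probability 2.5%. The protocol states 5% only for the vMRI sample size, without saying whether it is two-sided, and assigns no alpha to ADCOMS. For independent parts, 1 − (1 − 0.025)² = 1 − 0.9506 = 4.9%. A simulation of 100,000 trials (70 against 35 subjects, correlation between the Month 12 and Month 18 changes from 0 to 0.8) gives 4.7 to 4.9%.

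**5. Sensitivity of the own-baseline part to a shared shift.** Let both arms shift by s standard deviations of change, with no drug effect and n = 70 on drug. The chance of a significant favourable change from own baseline is 1 − Φ(1.96 − s√n). The documents give no value for s, so these rows are illustrations.

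| Shared shift s | 1.96 − s√70 | Own-baseline part favourable |
|---|---|---|
| 0 | 1.96 | 2.5% |
| +0.1 | 1.12 | 13% |
| +0.2 | 0.29 | 39% |
| +0.3 | −0.55 | 71% |
| −0.3 (decline) | 4.47 | below 0.01% |

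With n = 63 (70 less the protocol's 10% attrition), the three gains give 12%, 35% and 66%. In the simulation, the either-part reading gives 39 to 40% at s = +0.2 and 2.4 to 2.5% at s = −0.3.

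**6. The same check with placebo at both times.** A false favourable result occurs in 2.5% of trials at each time, in 3.9 to 4.9% if either time counts, and in about 0.1 to 1.1% if both must succeed. A shift shared by the arms cancels, so these figures do not depend on s.

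**The case against.** The strongest reply is that the section 10 sentence is not a decision rule. It describes what a positive effect would look like, in an assessments section, with no test, alpha or criterion. The formal hypothesis in section 12 already holds the controlled Month 12 comparison and would normally govern. This is right as far as it goes. A reader might infer that the trial has no controlled on-drug test of cognition, or that section 10 is its formal success rule. The documents support neither. What remains is that two sections disagree on the comparison and the analysis text does not clearly choose between them.

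The numbers also need limits:

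- A reader might quote 1 − 0.95² = 9.75% for two tests at 5%. That counts significant results against siponimod as well. Both parts of the sentence are directional, so 4.9% is the relevant figure.
- A reader might take the 13 to 71% as expected false-positive rates. They assume a net gain over 12 months, which the documents do not support and which sits badly with the decline described in section 2.1. If both arms decline, the own-baseline part adds almost no false positives. Its fault is then that it misses a real slowing.
- A reader might infer that a drug which slows decline would be called a failure. That is true of the own-baseline part only. A slowing that persists through washout could still show at Month 18. A benefit present on drug and lost by then would be missed.

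Finally, cognition is a tertiary objective in a Phase II safety study, so the consequence is limited. That bears on how serious the contradiction is, not on whether it exists.

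**Conclusion.** The sentence in section 10 is wrong as written. It contradicts section 12 and section 4 on the cognitive comparison, omits the controlled on-drug contrast, and offers an uncontrolled before-and-after change as evidence of drug effect. This finding rests on the text and needs no assumption.

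Its numerical size is modest where it can be stated: at most about 4.9% false favourable findings against 2.5% for one test, with no shift from baseline, two-sided 5% tests and non-negative correlation between the parts. That increase comes from having two chances. Section 12's two time points would carry a similar one (3.9 to 4.9%) if either sufficed. The particular fault of section 10 is its exposure to shared change from baseline, whose size the documents do not give.

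A reader might also infer that Month 18 should become merely supportive. The documents do not support that, since section 12 gives both times equal standing.

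The direction of the ADCOMS scale is a separate matter. The sentence treats higher scores as better, while the same section says that a higher ADAS-Cog score means more impairment. The contradiction described here remains once the sign is settled.

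**What to change.** Replace the sentence in section 10, Efficacy Assessments. Describe a positive cognitive effect as a siponimod-minus-placebo difference in ADCOMS change from baseline that favours siponimod, at Month 12 (end of dosing) and at Month 18 (off drug), in line with section 12. Remove the comparison with own baseline, and the wording that lets it stand as an alternative, as evidence of drug effect. Within-arm change may still be reported descriptively.

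The cost is one sentence. The ADCOMS components are already scheduled in both arms at Week 52 and Week 78, so no visit, measurement or subject is added.
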